
Response estimates are based on 2 studies of the effect of varenicline or placebo plus brief weekly individual behavioral treatment for smoking cessation in adolescent smokers with nicotine dependence of a similar age range. One reported modest medication adherence (63% took 100% of dispensed doses) and high dropout rate (45%) which may underlie low abstinence

rates (<10%) in both groups. We speculate that this trial under-estimates the therapeutic effect of varenicline for adolescent smoking cessation with more optimal treatment adherence. Additionally, potentially important participant characteristics, such as the proportion living with smokers, was not reported and may significantly impact abstinence outcomes in adolescents. In this trial, we will assess smoking and vaping in members of the household (or dorm) and in the primary peer group, and daily text message reminders to take medication and remotely observed dosing via emocha or REDCap will encourage medication adherence.

Continuous abstinence rates for weeks 9-12 of a 12-week intervention in the Pfizer report to the FDA in the varenicline arm ranged from 10-35%. Lowest abstinence rates (10%) were in older adolescents (ages 17-19) assigned to low dose varenicline (0.5 mg bid). In the proposed trial, adolescents who weigh >55kg, more likely amongst older adolescents, will be assigned to 1.0 mg bid as tolerated. Younger adolescents had numerically higher abstinence rates on 0.5 mg bid than 1.0 mg bid, regardless of weight, 16-21% versus 35%. This may have been due to tolerability issues. While there were no differences between any treatment arm in neuropsychiatric adverse events, the high dose group reported numerically more nausea, vomiting, and headache than the low dose and placebo groups. Those aged 17-19 with weight >55kg had better abstinence rates with 1.0 mg bid. Thus, we propose to dose by weight, not age, to employ flexible dosing as follows: All participants will be assessed for tolerability of 0.5 mg bid at the end of study week 1. Participants who weigh >55 kg who tolerate 0.5 bid with no complaints will be offered an increased dose of 1mg bid. Other participants will be continued at 0.5 mg bid.

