i. Varenicline Risks: Varenicline has been associated with significant adverse effects, including drowsiness and seizures, and must be used with caution while driving. Varenicline was previously thought to increase suicidality and neuropsychiatric side effects through similar mechanisms as bupropion and other antidepressants; however, the rate of neuropsychiatric adverse events has been shown to be no different between varenicline and placebo or bupropion or NRT patch in large-scale randomized controlled trial specifically examining these outcomes across an array of at-risk and general populations. Varenicline has not been approved for use in adolescents aged <18 years. However, recent studies have evaluated the pharmacology, safety, and tolerability of varenicline in adolescent smokers. The clinical pharmacology of varenicline in adolescent smokers was characterized in 1 single- and 2 multiple-dose pharmacokinetic (PK) studies in adolescent smokers. The most frequently reported adverse events in varenicline treated adolescent smokers were nausea, headache, vomiting, and dizziness. The incidence of nausea/vomiting increased with increasing varenicline exposure. Female adolescent smokers had a higher incidence of nausea relative to male adolescent smokers, regardless of dose, consistent with observations in adult smokers. Except for 1 case of severe nausea in a subject in the lowbody-weight group (< 55 kg) on varenicline 0.5 mg once daily, all AEs were mild or moderate in intensity and resolved during the study. Psychiatric adverse events considered to be treatmentrelated were abnormal dreams (n = 2) and mild, transient anger (n = 1). No participants discontinued medication or had their dosage reduced due to an adverse event. A 12-week varenicline trial from a Pfizer-sponsored multisite study in 307 adolescent smokers (12-19 years

of age) who were motivated to quit smoking reported no difference in tolerability between highdose (1 mg bid) or low-dose (0.5 mg bid) varenicline treatment versus placebo.

To minimize risk of nausea, dosing will be recommended with 240 ml of water, and it is recommended that subjects eat prior to dosing. It is recommended that there be at least 8 hours between the morning and evening doses. Dosing may be reduced to 0.5 mg bid, temporarily discontinued, or stopped for subjects due to adverse events (e.g., nausea).

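### Sections V and VI give incompatible dosing rules, and the Section VI rationale contradicts its own figures

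*Combined protocol and SAP*

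**What the plan says.** **Section VI, Statistical Design and Power.** The text summarises a manufacturer's report: "Continuous abstinence rates for weeks 9-12 of a 12-week intervention in the Pfizer report to the FDA in the varenicline arm ranged from 10-35" per cent. It gives three results by age band:

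- older, low dose: "Lowest abstinence rates (10%) were in older adolescents (ages 17-19) assigned to low dose varenicline (0.5 mg bid")
- younger: "Younger adolescents had numerically higher abstinence rates on 0.5 mg bid than 1.0 mg bid, regardless of weight, 16-21% versus 35" per cent, followed by "This may have been due to tolerability issues"
- older and heavier: "Those aged 17-19 with weight >55kg had better abstinence rates with 1.0 mg bid"

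It then concludes "Thus, we propose to dose by weight, not age, to employ flexible dosing as follows". Tolerability of 0.5 mg bid is assessed in all participants at the end of week 1. Those above 55 kg who tolerate it without complaint are offered 1 mg bid. For the rest, "Other participants will be continued at 0.5 mg bid".

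**Section V.b, dosing schedule.** There are three groups:

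- 16-17 years, 55 kg or less: 0.5 mg once daily for 7 days, then 0.5 mg bid for 11 weeks
- 16-17 years, above 55 kg: titration over 7 days, then 1 mg bid for 11 weeks
- 18 years and over, at any weight: the same titration, then 1 mg bid for 11 weeks

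The dose is lowered if 1 mg bid is poorly tolerated. No condition has to be met before the step up to 1 mg bid.

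**The concern.** A protocol should give one answer to the question of what dose a given participant receives. Here the answer depends on the section consulted. The varenicline arm is then not a single defined regimen, a departure from the dosing rule cannot be identified, and the primary contrast with placebo estimates the effect of an unspecified mix of two target doses.

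The rationale does not settle the matter, because its key sentence says one thing in words and the reverse in figures. A reader cannot tell from it which dose did better in younger adolescents, nor see why the result leads to a rule based on weight.

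**Working it through.** **1. The two rules side by side (dose from week 2)**

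| Participant | Section V.b | Section VI | Same? |
|---|---|---|---|
| 16-17 y, 55 kg or less | 0.5 mg bid | 0.5 mg bid | yes |
| 16-17 y, above 55 kg, no complaints on 0.5 mg bid | 1 mg bid | 1 mg bid offered | yes |
| 16-17 y, above 55 kg, complaints on 0.5 mg bid | 1 mg bid scheduled | 0.5 mg bid | no |
| 18+ y, 55 kg or less | 1 mg bid | 0.5 mg bid | no |
| 18+ y, above 55 kg, no complaints on 0.5 mg bid | 1 mg bid | 1 mg bid offered | yes |
| 18+ y, above 55 kg, complaints on 0.5 mg bid | 1 mg bid scheduled | 0.5 mg bid | no |

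In the three conflicting rows the target daily dose is 2 × 1 mg = 2 mg under Section V.b and 2 × 0.5 mg = 1 mg under Section VI. This two-fold difference lasts for 11 of the 12 weeks.

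**2. Direction of the younger-adolescent figures**

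- *Figures in the order the doses are named:* 0.5 mg bid = 16-21%, 1.0 mg bid = 35%. Difference (0.5 minus 1.0): 16 − 35 = −19 and 21 − 35 = −14 points. This contradicts the words.
- *Figures reversed:* 0.5 mg bid = 35%, 1.0 mg bid = 16-21%. Difference: 35 − 21 = +14 and 35 − 16 = +19 points. This agrees with the words, and with the tolerability explanation that follows them.

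**3. Stated response range.** The rates quoted are 10%, 16-21% and 35%. Their minimum is 10% and their maximum 35% under both readings, so the stated 10-35% does not change.

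**4. Does a weight rule follow from the efficacy results?**

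- *Order as written:* 1.0 mg bid did better in younger adolescents whatever their weight, and in those aged 17-19 above 55 kg. No weight split appears.
- *Order reversed:* 0.5 mg bid did better in younger adolescents whatever their weight, and 1.0 mg bid did better at 17-19 above 55 kg. The better dose then changes with age band.
- *Either way:* no dose comparison is reported for lighter 17-19-year-olds, so no contrast by weight within an age band is available.

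**The case against.** Several points can fairly be made for the plan.

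- **Section V.b is the operative schedule, and it allows the dose to be lowered.** That narrows the tolerability conflict but does not remove it. Section V.b reacts after 1 mg bid has been tried, while Section VI withholds 1 mg bid from anyone with complaints on the lower dose. The downward adjustment also does nothing for the conflict over participants aged 18 or over at 55 kg or less. Section VI words its rule as this trial's procedure, not as background.
- **A weight basis is stated elsewhere.** Section V.b reports that, in adolescents aged 12-17, exposure above 55 kg was comparable to that of adults on the same dose. At 55 kg or less it was about 40% higher on 0.5 mg bid. This stands, so the weight rule need not rest on the disputed sentence alone. But Section VI does not cite these data for its conclusion, and they do not cover participants aged 18 or over.

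Three stronger readings are tempting, and the documents do not support them.

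- **A figure behind the response estimates is wrong.** Reversing the order of the two figures removes the conflict without altering any number, and the 10-35% range is unaffected. The cited report is not available here, so an error in a number or in the wording can be neither shown nor ruled out.
- **The trial's power is affected.** Section VI says power was computed over a range of outcomes but gives no power or sample-size figure that uses dose-specific rates. Since 17-19 is the older band, only the 16-year-olds among the enrolled ages of 16-25 could belong to the younger band. Applying its rates to a whole arm would mislead.
- **Section VII contradicts the tolerability explanation.** It describes a study in adolescent smokers that "reported no difference in tolerability between highdose (1 mg bid) or low-dose (0.5 mg bid) varenicline treatment versus placebo". A numerical excess of nausea, vomiting and headache on the high dose is compatible with that summary, and Section VI offers tolerability only as a possible explanation.

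**Conclusion.** The point holds as a contradiction between two dosing rules, together with a rationale that is inconsistent within itself. Two groups get different instructions: participants aged 18 or over at 55 kg or less, and participants of any age above 55 kg with complaints on 0.5 mg bid. For them the target dose differs two-fold (1 mg against 2 mg a day) over 11 weeks. How many participants this covers cannot be worked out, because the documents give neither a weight distribution nor an expected rate of week-1 complaints.

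In the rationale, the words and the figures as ordered cannot both be right; the gap is 14 to 19 points in the wrong direction. Transposition is the likelier explanation, but that is inferred from the neighbouring sentences and not confirmed. Dosing by weight instead of age does not follow from the cited efficacy results on either reading. No error in the response range, power or sample size is established.

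**What to change.** 1. Reconcile Sections V.b and VI into one dosing rule. It should say explicitly whether age, weight and tolerability during week 1 each enter the decision, and how. State it once and cross-refer to it. Which rule or dose is right is for the investigators.
2. Check the younger-adolescent sentence against the cited report. Correct the words, the order or the figures as needed, and label each rate with its dose, age band and weight band.
3. Restate the basis for the rule. If it is the pharmacokinetic data in Section V.b, say so and say which ages they cover.
4. If participants have already been dosed, record which rule was applied to each, so that the regimen received can be described in the report.

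The cost is one check against a report the sponsor already cites, a wording amendment and, if item 4 applies, a look at dispensing records. No change to the analysis model or sample size is needed for this point.

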Hypothesis 2.1: We will use a linear model applied separately to repeated, continuous weekly assessments of nicotine withdrawal symptoms, craving, and negative mood symptoms. The linear model will be estimated using generalized estimating equations (GEE), providing estimates and standard errors robust to violations of distributional assumptions (e.g., normality), and heteroscedasticity. The model will be applied to the summed scores at each time point per subject. The analysis will be intent-to-treat with missing data imputed per the method specified above. The key confirmatory effect will be a dummy-coded contrast comparing placebo (coded as 0) against varenicline (coded as 1). Exploratory analyses will also be conducted to evaluate varenicline versus EUC and placebo versus EUC. The model will include covariates for a) change over time (two terms encoding linear and quadratic trends), b) baseline levels of the given outcome, as well as c) sex, environment (secondary school versus post-secondary school), and severity of nicotine dependence. Covariates will be standardized (mean-centered and scaled by the standard deviation). P-values will be adjusted to avoid multiple comparison issues using the Benjamini-Hochberg method.

Hypothesis 2.2: We will conduct a Fisher's exact test differences by randomized group in the number (%) of participants who endorse an AE at least once in the 12-week treatment period. We will evaluate frequent AEs (e.g., that occur in at least 5% of the participants at any point between weeks 1 through 12 of the trial).

Sensitivity analyses: We will conduct 3 sensitivity analyses to examine the robustness of our conclusion for efficacy.

- 1. We will test whether our conclusion on efficacy is robust to the inclusion/exclusion of the 3 covariates (biological sex, environment [secondary school vs. post-secondary school], and nicotine dependence severity) we therefore will rerun the analyses without the 3 covariates and examine whether the pooled estimate for the contrasts between varenicline, placebo, and/or EUC changes in sign and significance.
- 2. We will test whether our conclusion on efficacy is robust to the approach for imputation of missing data, examining whether the pooled estimate for the contrasts between varenicline, placebo, and/or EUC changes in sign and significance.
 - a. We will rerun the adjusted (i.e., with covariates) models on the observed data only.
 - b. We will rerun the adjusted models on a data set with the observed data and all missing outcome data imputed as non-abstinent.
- 3. We will test whether on conclusion on efficacy is robust to medication adherence by conducting a per protocol analysis. We will rerun the analyses only among participants who use varenicline on most days in the trial (e.g., 50-75%).

Software: All analyses will be conducted using the statistical software R (version 4.1.1).⁷⁵ Multiple imputation will be carried out using the R package 'mice' (version 3.13.0).⁷³ The GEE method will be implemented via the R package 'geepack' (version 1.3-2).⁷⁶

VII.. RISKS AND DISCOMFORTS

i. Varenicline Risks: Varenicline has been associated with significant adverse effects, including drowsiness and seizures, and must be used with caution while driving. Varenicline was previously thought to increase suicidality and neuropsychiatric side effects through similar mechanisms as bupropion and other antidepressants; however, the rate of neuropsychiatric adverse events has been shown to be no different between varenicline and placebo or bupropion or NRT patch in large-scale randomized controlled trial specifically examining these outcomes across an array of at-risk and general populations. Varenicline has not been approved for use in adolescents aged <18 years. However, recent studies have evaluated the pharmacology, safety, and tolerability of varenicline in adolescent smokers. The clinical pharmacology of varenicline in adolescent smokers was characterized in 1 single- and 2 multiple-dose pharmacokinetic (PK) studies in adolescent smokers. The most frequently reported adverse events in varenicline treated adolescent smokers were nausea, headache, vomiting, and dizziness. The incidence of nausea/vomiting increased with increasing varenicline exposure. Female adolescent smokers had a higher incidence of nausea relative to male adolescent smokers, regardless of dose, consistent with observations in adult smokers. Except for 1 case of severe nausea in a subject in the lowbody-weight group (< 55 kg) on varenicline 0.5 mg once daily, all AEs were mild or moderate in intensity and resolved during the study. Psychiatric adverse events considered to be treatmentrelated were abnormal dreams (n = 2) and mild, transient anger (n = 1). No participants discontinued medication or had their dosage reduced due to an adverse event. A 12-week varenicline trial from a Pfizer-sponsored multisite study in 307 adolescent smokers (12-19 years

of age) who were motivated to quit smoking reported no difference in tolerability between highdose (1 mg bid) or low-dose (0.5 mg bid) varenicline treatment versus placebo.

To minimize risk of nausea, dosing will be recommended with 240 ml of water, and it is recommended that subjects eat prior to dosing. It is recommended that there be at least 8 hours between the morning and evening doses. Dosing may be reduced to 0.5 mg bid, temporarily discontinued, or stopped for subjects due to adverse events (e.g., nausea).

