a. Study visits and parameters to be measured

The enrollment visit will be conducted in person and will include a detailed description of the study, informed consent/assent, assessments to confirm eligibility, assessments of vaping and other drug use behavior, and medical and psychiatric diagnostic and symptom assessments. Eligible, consented participants will then be scheduled for a baseline assessment visit where they will receive study medications (for those randomized to varenicline or placebo arms), weekly visits which will include assessments (all participants) as well as the behavioral vaping cessation sessions (for those randomized to varenicline or placebo arms), and monthly assessment visits. Following completion of the 12-week intervention period, participants will be scheduled for follow-up visits at weeks 16, 20, and 24. Study visits will be conducted at our MGB location, or in a private room at a participant's local library or current school. When conducting a study visit at a site external to MGH, study staff will obtain verbal permission from library/school administrators to conduct study visits at a given location. When obtaining permission to conduct a visit, no identifying or specific information regarding the participant or the study will be mentioned. All study visits can be conducted in person or virtually. We have piloted procedures and have a standard operating procedure for sending materials to conduct urine drug and pregnancy screening during virtual visits. Study staff will include instructions for participants to perform the tests and hold the assays up to their device's camera so study staff can record urine screening results. Height and weight will be recorded per participant's report for remote visits. Carbon monoxide will not be recorded for virtual visits, and we will rely on participant reported combusted tobacco use. Medication will be shipped via priority mail if a visit where medication is distributed is done virtually. Blood pressure and heart rate will not be collected if a visit is virtual, as these are not necessary measures in prescribing varenicline or part of our primary outcomes.

Time and Events Table

Time and Events

| | | | Follow-up period | | | | | | | | |
|--|------------|-------------|------------------|---------|-----------|---------|------------|----------|----------|----------|----------|

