The Alcohol Use Disorders Identification Test (AUDIT)^{61,62} was developed by the World Health Organization (WHO) as a simple screening tool to identify hazardous or harmful alcohol use. The AUDIT will be administered at the enrollment visit and at end of the treatment and follow-up phases of the study to detect change from baseline in harmful alcohol use.

The Cannabis Use Disorders Identification Test (CUDIT)⁶³ will be administered at the enrollment visit and at end of the treatment and follow-up phases of the study to detect change from baseline in symptoms of cannabis use disorder.

The Questionnaire of Vaping Craving (QVC)⁶⁴ is a brief, 10-item, valid and reliable measure of vaping craving that queries desire and intent to vape and anticipation of positive outcomes related to e-cigarette use that will be administered at enrollment, baseline, and weekly via REDCap.

Minnesota Nicotine Withdrawal Scale (MNWS)⁶⁵ is a valid, reliable, 9-item self-rated scale of urge to smoke (craving); depressed mood; irritability, frustration or anger; anxiety; difficulty concentrating; restlessness; increased appetite; difficulty going to sleep; difficulty staying asleep,

on an ordinal scale from 0 (not at all) to 4 (extreme). It will be administered at enrollment, baseline, and weekly via REDCap.

The Concise Health Risk Tracking Instrument (CHRT-SR)^{66,67} will be administered to provide a sensitive assessment for change in suicidality to supplement open-ended adverse events queries at each study visit during the treatment phase. The CHRT-SR is a reliable and valid measure for examining severity of suicidal thoughts and associated risk factors and is sensitive to change in adolescents. It will be administered at baseline and each monthly assessment visit during the treatment and follow-up phases. Clinically trained study staff will follow-up on any positive responses.

The Mood and Anxiety Symptoms Questionnaire (MASQ-D30)⁶⁸ is a 30-item adaptation of the 96 item MASQ that is a quick, valid, and reliable assessment of depression and anxiety in adolescents that will be administered at enrollment, baseline, and each assessment visit.

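### Hypothesis 2.1 appears to adjust only for the Week 0 score, although each symptom scale is also collected at enrollment; entering both scores separately may gain some precision at almost no cost

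*Combined protocol and SAP*

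**What the plan says.** Section VI, Statistical method, Hypothesis 2.1, plans a linear GEE model for "repeated, continuous weekly assessments of nicotine withdrawal symptoms, craving, and negative mood symptoms". On covariates it says: "The model will include covariates for a) change over time (two terms encoding linear and quadratic trends), b) baseline levels of the given outcome"; sex, school environment and dependence severity are then added. The varenicline-placebo contrast is designated as confirmatory, and p-values are adjusted by Benjamini-Hochberg.

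Section V.f sets the measurement schedule:
- MNWS (withdrawal): "It will be administered at enrollment, baseline, and weekly via REDCap".
- QVC (craving): "anticipation of positive outcomes related to e-cigarette use that will be administered at enrollment, baseline, and weekly via REDCap".
- MASQ-D30 (mood): "assessment of depression and anxiety in adolescents that will be administered at enrollment, baseline, and each assessment visit".

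The Time and Events Table marks all three scales at both Enrollment and BL (Wk0). Section V.a says participants are "scheduled for a baseline assessment visit where they will receive study medications", and the table shows randomization and first drug distribution at that visit. None of the three scales is an inclusion or exclusion criterion in Section III.

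**The concern.** Each scale has two pre-treatment scores, and the plan appears to use one. A single self-report score is a noisy measure of a participant's usual level. The outcome in the model behaves like an average over up to 12 weekly scores, so much of its residual variance can be a stable between-person level that a second pre-treatment reading helps to remove. If so, the standard errors of the contrast are larger than the collected data require.

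The covariate is also not tied to a visit. The plan uses the word baseline loosely elsewhere: the missing-data text places the dependence score at the baseline visit, whereas the Time and Events Table shows the ECDI before treatment only at enrollment. Naming the scores in advance also removes a choice that could otherwise be made after the data are seen.

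**Working it through.** **Nothing to reproduce.** The documents print no power, SD, correlation or effect size for Hypothesis 2.1. The check is therefore a comparison of designs.

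**Inputs from the documents.** Two pre-dose scores per scale. On-treatment scores: k = 12 for MNWS and QVC (weeks 1-12) and k = 3 for MASQ-D30 (weeks 4, 8, 12 in the table, although the model text calls mood weekly). Up to 240 randomized 1:1:1, so up to 80 per arm; the number per arm cancels from every ratio below.

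**Assumptions.** All correlations, the enrollment-to-baseline gap (1, 2 or 4 weeks), complete data, and no allowance for the other covariates.

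**Formula.** Let w be the correlation between two scores in the same period (both pre-treatment or both on treatment), c the correlation between a pre-treatment and an on-treatment score, and p the number of pre-treatment scores. The adjusted variance of a participant's mean on-treatment score, in units of the single-score variance, is

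V = (1 + (k-1)w)/k - p c²/(1 + (p-1)w).

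**1. All correlations equal (w = c = r).** Example, k = 12, r = 0.5: (1 + 11×0.5)/12 = 0.5417. One score: 0.5417 - 0.25 = 0.2917. Two scores: 0.5417 - 2×0.25/1.5 = 0.2083. Cut: 1 - 0.2083/0.2917 = 28.6%.

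| r | k = 12: one, two, cut | k = 3: one, two, cut |
|---|---|---|
| 0.4 | 0.2900, 0.2214, 23.6% | 0.4400, 0.3714, 15.6% |
| 0.5 | 0.2917, 0.2083, 28.6% | 0.4167, 0.3333, 20.0% |
| 0.6 | 0.2733, 0.1833, 32.9% | 0.3733, 0.2833, 24.1% |
| 0.7 | 0.2350, 0.1485, 36.8% | 0.3100, 0.2235, 27.9% |

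A 600-run simulation at r = 0.5, k = 12 gave a mean standard error of 0.085 with one score and 0.072 with two, in line with the formula.

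**2. Pre-to-post correlation lower than within-period correlation (k = 12).**
- w = 0.6, c = 0.4: 0.6333 - 0.16 = 0.4733; 0.6333 - 0.32/1.6 = 0.4333; cut 8.5%.
- w = 0.6, c = 0.3: 0.5433 to 0.5208; cut 4.1%.
- w = 0.7, c = 0.4: 0.5650 to 0.5368; cut 5.0%.

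The same three cases with k = 3 give 7.0%, 3.5% and 4.4%.

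**3. Correlation decaying with the gap d in weeks.** Here V = var(mean on-treatment score) - g′B⁻¹g, where B is the covariance matrix of the pre-treatment covariates used and g their covariances with the mean on-treatment score. Ranges cover gaps of 1 to 4 weeks; a negative cut is a loss.

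| Correlation at d > 0 | Both entered, k = 12 | Both entered, k = 3 | Mean of the two, k = 12 |
|---|---|---|---|
| 0.4 + 0.3exp(-d/3) | 12.7 to 15.1% | 8.9 to 11.6% | 12.5 to 14.5% |
| 0.3 + 0.4×0.8^d | 8.7 to 8.9% | 5.8 to 6.6% | 7.4 to 8.6% |
| 0.2 + 0.5exp(-d/6) | 5.2 to 6.7% | 3.6 to 4.0% | 2.7 to 6.3% |
| 0.8×0.95^d | 4.6 to 8.6% | 3.0 to 5.5% | -0.3 to 8.1% |
| 0.2 + 0.6×0.8^d | 3.7 to 3.8% | 2.4 to 2.9% | 0.7 to 3.2% |
| 0.1 + 0.7exp(-d/6) | 1.6 to 2.8% | 1.1 to 1.5% | -2.9 to 2.0% |
| 0.9^d, pure AR(1) | 0% | 0% | -12.6 to -3.7% |
| 0.5 + 0.2×0.8^d, nearly flat | 18.4 to 19.4% | 13.2 to 14.8% | 18.3 to 18.8% |

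Entering both scores never increased the variance in any case tried. Averaging them did so in three of the eight patterns.

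**The case against.** The strongest reply is that nothing is wrong with the plan. One pre-treatment score is a valid covariate, Aim 2 is secondary, and the primary abstinence outcome is untouched. That stands, and it limits the point to efficiency.

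A second reply is that the model text names neither a visit nor a number of scores. A reader might infer that the plan states it discards the enrollment score; it does not. Week 0 alone is the natural reading because enrollment and baseline are separate named visits, but it remains an inference.

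A third concerns size. A reader might carry away the equal-correlation cut of 24-37%, or its equivalent: a weekly-scale contrast with 80% power rising to about 91-94% at r of 0.5 to 0.7. The documents do not support that as an expectation. Participants in every arm are advised or supported to quit between the pre-treatment and on-treatment scores, and Section VII says abstinence itself can bring withdrawal symptoms for up to 4 weeks. Pre-to-post correlation may therefore be lower than correlation within either period, as in step 2. The power figures also ignore the other covariates and the Benjamini-Hochberg adjustment, and they presume the maximum sample size.

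Last, averaging the two scores looks like the obvious remedy, but step 3 shows that it can make the contrast less precise.

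**Conclusion.** The point holds as an efficiency improvement to a secondary analysis. Two pre-dose scores exist for each scale, the model on its natural reading uses one, and the other has no stated role. There is no bias and no invalid test.

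The gain from entering both scores is about 0-15% of the variance of the varenicline-placebo contrast under most of the decaying or modest pre-to-post correlations tried, and 13-19% under one nearly flat pattern. It reaches 24-37% for the weekly scales, or 16-28% for the monthly mood scale, only if all correlations are equal at 0.4 to 0.7. In standard-error terms, a 15% variance cut is 1 - √0.85 = 7.8%. Every figure rests on assumed correlations, an assumed visit gap and complete data, so no single gain should be promised.

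**What to change.** Before unblinding, replace the baseline-level covariate in the Hypothesis 2.1 text with: *the enrollment score and the baseline (Wk0) score of the given outcome, entered as two separate covariates; if one is missing, it is imputed from the other pre-treatment score and the baseline covariates.* Do not mandate the mean of the two scores.

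The cost is one sentence in the analysis plan and one extra degree of freedom per model, small against up to 160 participants in the two drug arms. No new data, visits or participants are needed. If the sponsor prefers the Week 0 score alone, the text should say so.
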